The few RCTs that have compared LFS to non-surgical care for LBP  are limited by small samples, cross-over, selection bias and widely varying non-surgical care. Studies  conclude no clear advantage of fusion but show modest benefits for function, pain and general health. The only previous UK trial  concluded there was no clear evidence that LFS was better than intensive rehabilitation although the trial included a mix of patients with chronic LBP, including those with spondylolisthesis and previous laminectomy surgery. That trial changed practice, and better quality conservative treatment pathways now exist (but are not always readily available), and no work has examined the more contemporary issue of whether LFS has a place in treating patients who have not responded to recommended conservative care interventions. The most recent systematic review  and meta-analysis of 6 RCTs concluded LFS is no better than non-operative care for pain and disability at short, or long term follow-up. It also concluded that previous RCTs had relatively 'lax' patient inclusion criteria and advised future RCTs to better define their selection criteria.

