## 13.2. Best Conservative Care (BCC) (usual care/ comparator)

All participants randomised to the BCC control arm will be reviewed by a senior spinal practitioner or pain physician, (usually a senior MSK physiotherapist), with experience in delivering personalised spinal care utilising shared decision making (SDM) with links to a wider Multi-Disciplinary Team (MDT). This will include a clinical evaluation of imaging findings, a formulation of the participants case and a review of previous treatment effectiveness. An individually tailored package of care based on the participant's goals and expectations will be agreed through Shared Decision Making (SDM) and labelled as 'Personalised Spinal Care'. In this way the BCC will be personalised and attractive to potential participants.

Treatment options within BCC will be aligned with national guidance (NICE and the NLBRPP) and include at least one of the following:

- 1. Advice (active self-management, pacing, diagnosis, aetiology, return to work etc.)
- 2. Analgesia
- 3. Exercise
- 4. Manual Therapy (manipulation, joint/soft tissue mobilisation)
- 5. Combined Physical & Psychological Programme
- 6. Pain Management Programme
- 7. Psychological Therapy (e.g. Psychologist, Cognitive Behaviour Therapy, ACT, Behavioural Therapist, Counselling)
- 8. Interventional Pain Management for low back pain (e.g. medial branch block/radiofrequency denervation)
- 9. Signposting to other health material or interventions (e.g. Dietician, smoking cessation, social prescribing)

Complex healthcare interventions such as those utilised for the conservative care of those with persistent LBP are frequently composed of multiple independent and interdependent elements. Therefore, slight variations from those listed above but within the accepted framework are

acceptable to reflect local service provision. We have worked with the FORENSIC-UK CAG to closely define essential and preferred treatment components.

If the participant randomised to BCC is placed on a long wait list for BCC treatment options they will continue with the relevant NHS Trust routine care with monitoring until they can commence their BCC treatments.

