#### 17.2. Data Collection

## 17.2.1. Baseline

A baseline questionnaire will be completed by participants at a face-to-face appointment, over the telephone, videoconference or via the post. The questionnaire will include the following outcome measures: Oswestry Disability Index (ODI), Quality of life (EQ-5D-5L) only, we have omitted the EQ-VAS scale for this study, Pain Self-efficacy Questionnaire (PSEQ), Patient Health Questionnaire (PHQ8), Tampa Scale of Kinesiophobia (TSK), Work status/work type.

In order to include variables that may be potential moderators of outcome from the treatments offered in the trial, to support future secondary trial analyses of the combined trial datasets from the UK and Australia, we will collect data on the following: smoking, workers' compensation claim, heavy physical demands at work, medication use for LBP, body mass index (Hayden JA et al 2020) via Participant height and weight collected data, duration of LBP, co-morbidities which may include: diabetes, heart problems, high blood pressure, anxiety, depression, stress, neurological conditions, chronic fatigue (ME, Fibromyalgia), COPD, asthma, breathing problems. We will also ask about education, pain following movement, use of a pain mannequin diagram to identify area of pain, low back pain characteristic, severity of low back pain on movement, effects of changing position on low back pain, ethnicity, work status and type.

Information will also be collected if the participant has previously had a discectomy or decompression.

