## 17.3. Communication with study participants by the central study team

At 6-, 12- and 24-months participants will be sent either a postal questionnaire or an email from the central study team with a personalised link asking them to complete the electronic questionnaire, depending on their stated preference. If the paper-based version of the questionnaire is requested, this will be sent to participants to complete and return to the Trial Office in a prepaid envelope.

Reminders will be sent to participants who do not respond to the initial follow up questionnaires by post or email with an electronic link (dependant on participant preference) at 2 weeks and a further 2 weeks later if there is no response. This data would be entered onto the trial database by the data entry personnel at the Trial Office.

Telephone follow-up will be used (2 weeks after), as applicable, to contact those who do not respond to either the initial or reminder questionnaire. Telephone and email follow-up will also be used to collect a core set of questionnaire items for the Oswestry Disability Index questionnaire

(primary outcome), and other outcome data, if these have not been fully completed on the returned questionnaire.

Participants will be contacted with regular newsletters (by email or post) to disseminate study progress and maintain engagement in the study.

Assessments	Screening	Baseline	Intervention LFS/BCC	6months	12months	24months (Primary outcome timepoint)
Eligibility	Х					
Informed Consent		х				
QRI Consent *		Х*				
Demographics		х				
Randomisation		х				
Intervention Details			Х			
Participant Completed Questionna	ires:					-
Oswestry Disability Index (ODI)		х		х	Х	x
Quality of life (EQ-5D-5L)		х		х	Х	х
Depression (PHQ8)		х		х	Х	х
Fear of movement beliefs (TSK)		х		х	Х	х
Pain Self-efficacy (PSEQ)		х		х	Х	x
Global Perceived Effect Scale (GPE)		х		х	Х	x
Healthcare Resource Use				х	х	х
Treatment Satisfaction						x
Work Status		х		х	Х	х
LBP severity (NRS) [over 24 months]		х		х	х	x
Safety reporting				х	Х	x
Complication data				х	Х	x
CT Scan at 24months post randomisation						x
Participant interviews **		X**				

Table 2: Scheduled assessments/outcome collection for the study

\*Optional for integrated information study

\*\* Optional for integrated Information Study

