#### 19. IMAGING

Data will be collected on any MRI, SPECT CT, standing X-Rays and other imaging that has been undertaken in the 12m pre-randomisation.

For participants randomised to the surgery arm they will undergo Image intensification during the surgical procedure.

Standard Computed Tomography (CT) scans for patients randomised to surgery will be carried out at the 24-month follow-up time point as part of the fidelity assessment. The clinical team at the local site will review and complete a CRF to indicate whether spinal fusion was achieved.

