# 23.1. Within trial economic evaluation

An economic evaluation will be undertaken alongside the trial to estimate the cost effectiveness of LFS versus BCC. This will take the form of an incremental cost-utility analysis to estimate cost per quality adjusted life year (QALY) and incremental net benefit at 24 months follow-up, using patient level data on costs and outcomes from the trial. The base-case analysis will be from an NHS perspective, with an additional analysis from a societal perspective taking into account out of pocket expenditure and productivity losses. In order to calculate QALYs, the EQ-5D-5L will be included in the questionnaires to participants at baseline, 6, 12 and 24 months. The UK mapping value  set will be applied to participant responses to obtain utility scores, in line with current NICE recommendations.

Data will be collected within the trial to calculate the cost of each LFS undertaken. Information will be collected via the surgery CRF on the type of surgery undertaken and length of stay post-operation and will be used to attach the relevant Healthcare Resource Group (HRG) code from the most recent NHS reference costs. Any additional post-operative resource use will be collected via the participant completed follow-up questionnaires. For each participant allocated to BCC, their package of care will be recorded, including types of care (e.g. a course of physiotherapy, multidisciplinary pain management programme), mode and number of sessions. The per-person cost of BCC will then be calculated.

Information on all other LBP-related resource use will be collected via participant questionnaires at 6, 12 and 24 months. Questions will request information regarding primary and secondary care visits (e.g. GP, nurse, physiotherapy, consultant, specialist, outpatient clinic), visits to other healthcare professionals including non-NHS, prescribed analgesics, tests and investigations, further treatment including surgery and injections. The recall period in each questionnaire will be the previous 6 or 12 months. Unit costs from standard UK sources will be sought for all healthcare resource use items.

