## 23.2. Health economics analysis

QALYs will be calculated using responses to the EQ-5D-5L, using the "area under the curve" approach. Unit costs will be applied to all healthcare resource use items, and mean resource use (for each category of healthcare usage) and mean total costs will be calculated for all trial participants. The per participant cost of each surgical procedure will also be determined, with the mean cost per type of LFS also estimated. Analysis of productivity losses will use the human capital approach, and the self-reported days of absence will be multiplied by the respondent-specific wage rate. The human capital approach assumes that the value of lost work is equal to the amount of resources an individual would have been paid to do that work, and values productivity losses as a result of morbidity (or mortality) by measuring time lost from work and multiplying this with the gross wage of the person.

The final statistical model for analysis will be selected following data examination and measures of model fit. Multiple imputation will be used to impute all missing values for the EQ-5D-5L and total cost estimates for non-responders. A cost-consequence analysis will initially be reported, describing all the important results relating to costs and consequences (across the full range of clinical outcomes). Incremental cost-utility analysis will then be undertaken to estimate the incremental cost per QALY gained, adjusting for baseline covariates. The robustness of the results will be explored using sensitivity analysis. This will explore uncertainties in the trial-based data itself, the methods employed to analyse the data, the population and the generalisability of the results to other settings. Cost-effectiveness acceptability curves will also be produced to reflect the probability that LFS is cost-effective at different cost per QALY willingness to pay thresholds, compared to BCC.

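### Baseline data cover LBP medication, recent imaging and earlier decompression or discectomy, but no stated item covers prior non-drug conservative care or healthcare use before entry

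*Protocol*

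**What the plan says.** Section 17.2.1 sets out the baseline data: the patient-reported scales, work status, and a list of possible moderators for later analysis of the combined UK and Australian data. That list includes "heavy physical demands at work, medication use for LBP, body mass index". The section ends: "Information will also be collected if the participant has previously had a discectomy or decompression". Section 19 adds one more item of earlier care: "Data will be collected on any MRI, SPECT CT, standing X-Rays and other imaging that has been undertaken in the 12m pre-randomisation".

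In Table 2 (Section 17.3) the row "Healthcare Resource Use" is marked at 6, 12 and 24 months and blank at baseline. Section 23.1 agrees: "Information on all other LBP-related resource use will be collected via participant questionnaires at 6, 12 and 24 months". The recall period given there is 6 or 12 months.

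Section 23.2 plans an incremental cost-utility analysis "to estimate the incremental cost per QALY gained, adjusting for baseline covariates", without naming the covariates, and multiple imputation of missing EQ-5D-5L values and of total costs for non-responders. Section 23 leaves full details to a Health Economic Analysis Plan, which is not at hand.

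The population is defined by earlier treatment. Section 8 presents the open question as "whether LFS has a place in treating patients who have not responded to recommended conservative care interventions", and Section 11.3 lists qualifying treatments: physical therapy, psychological therapy, multidisciplinary care, specialist medical care, medial branch block or denervation, and analgesia.

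**The concern.** Failure of earlier conservative care is what sets this trial apart from its predecessors (Sections 8 and 11.4). A reader of the results will want to know what that care was and whether the arms were alike in it. Of the treatments listed in Section 11.3, only analgesia has a clear counterpart among the stated baseline items.

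Two features of the protocol make this matter more. First, the options within BCC (Section 13.2) overlap with the qualifying treatments, so without a treatment history one cannot tell whether BCC offered something new or repeated what had already failed. Second, the prior-care requirement is worded inconsistently, so a recorded history would be the only way to show which standard participants met.

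On the economic side, use of care before entry is a natural predictor of later use. If it is not collected before randomisation, no later analysis plan can supply it.

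**Working it through.** **1. Is the information collected anywhere else before randomisation?**

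| Possible source | What it gives |
|---|---|
| Section 17.2.1, baseline list | LBP medication, previous discectomy or decompression; no physical, psychological, multidisciplinary or specialist care, no blocks or denervation |
| Section 19, imaging | Imaging in the previous 12 months |
| Section 12.2, screening log | Reasons for ineligibility; for eligible patients, ethnicity, gender and deprivation score |
| Section 13.2, BCC review | "a review of previous treatment effectiveness": after randomisation, BCC arm only, described as clinical care and not as data capture |
| Section 23.1, questionnaires | First at 6 months after randomisation; a 6-month recall there does not reach back before entry |
| Section 28.1, routine-data linkage | Starts at consent or randomisation and depends on further funding |

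None supplies pre-randomisation healthcare use, and none is stated to supply prior non-drug treatment. Section 24.4 adds that no study data are held outside the CRF.

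**2. The prior-care requirement, side by side.** The text closing Section 11.3 expects at least one of the listed treatments. Sections 11.2 and 11.4 expect core therapy and, in addition, a further elevated therapy that is available locally. A patient who has had one listed treatment only can meet the first and fail the second. The passages must be reconciled.

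**3. What a baseline value could be worth.** The protocol states no figure on this point, so there is none to reproduce. Let r be the within-arm correlation between resource use before entry and the later cost. Linear adjustment for the baseline value multiplies the variance of the between-arm difference by 1 − r², so the interval narrows by 1 − √(1 − r²). The protocol gives no r; the range is assumed.

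| r (assumed) | 1 − r² | √(1 − r²) | Interval narrower by |
|---|---|---|---|
| 0.1 | 0.99 | 0.995 | 0.5% |
| 0.2 | 0.96 | 0.980 | 2.0% |
| 0.3 | 0.91 | 0.954 | 4.6% |
| 0.5 | 0.75 | 0.866 | 13.4% |

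The sample size rests on the ODI (Section 22.2) and does not change.

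**The case against.** The strongest reply is that silence is not proof of absence. Section 17.2.1 is not a closed list: the pain NRS is marked at baseline in Table 2 but is not named there, and recent imaging appears only in Section 19. Prior treatment is an eligibility criterion with no waivers (Section 11.5), hospital records are to be summarised into the CRF (Section 24.1), and the eligibility form may already hold the treatment history. This stands for the treatment history, and the fix allows for it. It does not stand for healthcare use, where Table 2 and Section 23.1 agree on the time points and omit baseline.

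A second reply is that nothing in the analysis requires a baseline cost. Healthcare use is a secondary outcome, and a reader might infer from Section 22.3, which models secondary outcomes in line with the primary analysis, that a matching baseline is required. It is not: treatment satisfaction, measured only at 24 months, falls under the same sentence and can have no baseline. Likewise, the covariate adjustment in Section 23.2 can be met with baseline EQ-5D-5L and the stratification factors. Both points stand.

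Third, the gain may be small. Total cost includes the surgery and BCC packages taken from intervention forms, and use before entry may predict those poorly. Section 22.9 also says that only essential items are collected, and Section 22.5 names no prior-care subgroup. These are fair reasons to treat the proposal as optional.

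**Conclusion.** The gap is real but narrow. Apart from LBP medication, previous discectomy or decompression, and imaging in the preceding 12 months, the protocol specifies no baseline record of prior conservative treatment, and it does not schedule healthcare resource use at baseline.

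Three stronger readings are not supported:

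- **That nothing about earlier care is recorded.** The three items above are.
- **That the trial cannot show who its participants are.** Eligibility is confirmed by clinicians, and pain severity, duration of LBP and comorbidities are also described. What the report could not give, on the items stated, is the type and amount of prior non-drug care by arm.
- **That the cost comparison is biased.** Allocation is randomised, so the loss is of precision, of a check on chance imbalance, and of a useful imputation predictor.

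The gain in interval width runs from about 0.5% to 13% for r between 0.1 and 0.5, all assumed. The descriptive gap needs no such assumption, only that the treatment history is not already on an unseen form. This is a worthwhile low-cost improvement; the primary outcome and its power are untouched.

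**What to change.** 1. Add the 6-month resource-use questions to the baseline questionnaire, with recall set to the six months before entry, and mark the row at baseline in Table 2 and in Section 23.1.
2. Add a tick list of the Section 11.3 treatments to the baseline or eligibility form, completed before randomisation in both arms, or state that the form already has it.
3. Name baseline resource use as a covariate and as an imputation predictor for healthcare use and total cost, and report prior treatment by arm.
4. Reconcile the statements of the prior-care requirement in Sections 11.2, 11.3 and 11.4.

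The cost is one to two extra pages at baseline, mostly questions already written, and a slightly longer visit. No extra participants, staff or procedures are needed. Anyone randomised before the change will lack the values and must be handled as having missing covariates, which is a reason to make the change early.

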## 17.2.2. Intervention

An intervention case report form (CRF) will be used to document the interventions and monitor compliance with the intervention guidelines. For the Lumbar Fusion Surgery (LFS) group, information will be collected on type of surgery undertaken and length of stay post-operation and will be used to attach the relevant Healthcare Resource Group (HRG) code from the most recent NHS reference costs. Any additional post-operative resource use will be collected via the participant completed follow-up questionnaires.

For the Best Conservative Care (BCC) group the package of care will be recorded, including types of care (e.g. a course of physiotherapy, multidisciplinary pain management programme, medial branch block, facet ablation, self-management, signpost to other health related services etc), and number of sessions. See section 13: Best Conservative Care (BCC).

## 17.2.3. Follow-up assessments/subsequent visits

Follow-up will involve:

- Participant questionnaires at 6-, 12- and 24-months post randomisation
- Medical notes check (local sites) to record complications
- Appointment for a follow-up CT scan at 24 months post-randomisation for participants who have had LFS only.

#### Participant questionnaires

A study questionnaire will be sent to participants for completion at 6-, 12- and 24-months post randomisation. These will be sent by the central study team and can be completed by post or online. The questionnaire will include the following:

- LBP-related physical function using the Oswestry Disability Index (ODI)
- Quality of life (EQ-5D-5L)
- Pain Self Efficacy Questionnaire (PSEQ)
- Change to back pain measure using Global Perceived Effect (GPE)
- Patient Health Questionnaire (PHQ8)
- Fear of movement (fear avoidance) beliefs (TSK)
- Healthcare resources use (NHS and non-NHS) including surgery, conservative care, concurrent treatments (including analgesia)
- Work Status (days off work)
- Participant Intervention Adherence
- Treatment Satisfaction at 24m only

In addition, LBP severity (Numerical Rating Scale) will be collected using monthly SMS messages which will contain a link to enter a score or by email or by paper version via the post (participant preference) to capture data on low back pain severity. A reminder email/SMS message will be sent 2 days after the initial message, sent from the central study team to participants over the 24 months follow-up period. We will follow up with a postal reminder by post (for participants wishing to complete the LBP pain severity on paper) two weeks after the initial postal form was sent to accommodate postal delivery.

All postal questionnaires including LBP pain severity will be accompanied with a self-addressed stamped return envelope.

## 17.3. Communication with study participants by the central study team

At 6-, 12- and 24-months participants will be sent either a postal questionnaire or an email from the central study team with a personalised link asking them to complete the electronic questionnaire, depending on their stated preference. If the paper-based version of the questionnaire is requested, this will be sent to participants to complete and return to the Trial Office in a prepaid envelope.

Reminders will be sent to participants who do not respond to the initial follow up questionnaires by post or email with an electronic link (dependant on participant preference) at 2 weeks and a further 2 weeks later if there is no response. This data would be entered onto the trial database by the data entry personnel at the Trial Office.

Telephone follow-up will be used (2 weeks after), as applicable, to contact those who do not respond to either the initial or reminder questionnaire. Telephone and email follow-up will also be used to collect a core set of questionnaire items for the Oswestry Disability Index questionnaire

(primary outcome), and other outcome data, if these have not been fully completed on the returned questionnaire.

Participants will be contacted with regular newsletters (by email or post) to disseminate study progress and maintain engagement in the study.

Assessments	Screening	Baseline	Intervention LFS/BCC	6months	12months	24months (Primary outcome timepoint)
Eligibility	Х					
Informed Consent		х				
QRI Consent *		Х*				
Demographics		х				
Randomisation		х				
Intervention Details			Х			
Participant Completed Questionna	ires:					-
Oswestry Disability Index (ODI)		х		х	Х	x
Quality of life (EQ-5D-5L)		х		х	Х	х
Depression (PHQ8)		х		х	Х	х
Fear of movement beliefs (TSK)		х		х	Х	х
Pain Self-efficacy (PSEQ)		х		х	Х	x
Global Perceived Effect Scale (GPE)		х		х	Х	x
Healthcare Resource Use				х	х	х
Treatment Satisfaction						x
Work Status		х		х	Х	х
LBP severity (NRS) [over 24 months]		х		х	х	x
Safety reporting				х	Х	x
Complication data				х	Х	x
CT Scan at 24months post randomisation						x
Participant interviews **		X**				

Table 2: Scheduled assessments/outcome collection for the study

\*Optional for integrated information study

\*\* Optional for integrated Information Study

